Presently, the exact mechanism of LLLTT remains enigmatic, and it remains unclear the impact this technology can have on genetic aberrations. Nevertheless, preliminary studies have shown, subsequent to LLLTT, upregulation of cell bioenergetics and sequential influence on intra-cellular secondary cascades. Clinical outcomes include nerve regeneration, increased neurotransmitter release, growth factor synthesis, and neovascularization to name a few. Accordingly, auspicious positioning of laser along impaired regions of an autistic brain could elicit a positive therapeutic outcome.

SUPPORTIVE CLINICAL DATA: ERCHONIA® HLS FEASIBILITY PROOF OF CONCEPT TRIAL

BACKGROUND

In September 2012, a **feasibility proof of concept trial** based on the design - including device specifications and output, and treatment administration protocol parameters - was completed that evaluated the exact same indication proposed in this pivotal clinical trial. The feasibility proof of concept trial successfully established safety and potential effectiveness of the Erchonia® HLS Laser Device for the proposed indication for use of: "The Erchonia® HLS laser device is indicated to improve the symptoms of irritability associated with autistic disorder in children and adolescents aged five to seventeen years, inclusive."

STUDY DESIGN

The feasibility proof of concept trial was conducted as a pilot study that employed the same parameters of the currently proposed full-scale pivotal trial protocol including the Erchonia® HLS Laser Device and its output parameters, the device application with respect to the

treatment administration protocol (number, frequency and duration of treatment administrations, etc.); and the study qualification enrollment criteria.

As the study was conducted as a feasibility study, all subjects received the active device treatments with the Erchonia® HLS Laser Device.

The Aberrant Behavior Checklist (ABC) assessment tool was administered at Baseline evaluation (before receiving the first laser treatment administration) and at study Endpoint evaluation (after completion of the entire laser treatment administration protocol).

SUBJECT SAMPLE

In the feasibility study, eleven (9 male and 2 female) children and adolescents aged from 5 years 4 months to 16 years 10 months with autistic disorder who satisfied all of the study qualification criteria were enrolled.

RESULTS

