5. An individual for whom the caregiver decides not to permit participation in the study will continue to work with the physician on the ASD treatment plan goals for the minor patient.

Compensation

A subject or his or her caregiver(s) will not be offered money or any other form of compensation to participate in the clinical study; however, there will also not be any charge for the cost of the study treatments with the Erchonia® HLS laser device or for the cost of any other directly-related evaluations or measurements that occur as part of the subject's participation in this study.

Subject Sample Size

There will be 40 qualified subjects enrolled in this clinical study:

- 20 subjects in the test group
- 20 subjects in the control group

Rationale and Justification for Sample Size

This study is powered to compare one active arm with placebo. Sample size calculation is based on the primary efficacy measure of the mean change from study baseline to endpoint (end of the 4-week treatment period) in the Aberrant Behavior Checklist (ABC) Irritability Subscale score adjusted for the baseline ABC Irritability Subscale score.

Based on detecting a mean difference of -8.5 points between test and placebo groups in the change in ABC Irritability Subscale score adjusted for the baseline ABC Irritability Subscale score being considered clinically relevant with a SD of 8.9, a two-sided test with 80% power and a 5% level of significance, the number of subjects needed per treatment group is 18.

From here, it is anticipated that about one-tenth of subjects overall may withdraw or be terminated from the study prior to completion for various reasons. Therefore, the following formula is used to determine the final needed starting sample size for each procedure arm:

Final sample size = sample size X $1/(1-d)$; where $d = \# \text{ expected dropouts}/\# \text{ subjects enrolled}$.

Final sample size = $18 \times 1/(1-0.11)$; where $d = 2/19$

Final sample size = $18 \times 1/0.89 = 18 \times 1.124 = 20$ subjects per treatment group.

Therefore, a minimum starting sample size of 20 subjects in each treatment group (40 subjects in total) is needed to ensure that a sufficient number remains at study endpoint (18 evaluable subjects per treatment group) for any significant differences found between treatment groups to be considered statistically valid and representative of the general population being sampled.

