6 MONTHS: ACTIVE TREATMENT GROUP ONLY

Following the final enrolled subject's completion of the Week 8 Post-Treatment Evaluation, study blinding will be broken. Subjects who had been assigned to the active treatment group will take part in the 6 months post-procedure evaluation visit to gain a sense of duration of the treatment effect. At this visit, the following study measures will be recorded:

- Aberrant Behavior Checklist (ABC)
- Clinical Global Impressions (CGI)
- Medication and therapy use review
- Adverse events evaluation

PLACEBO SUBJECTS POST-STUDY CROSS-OVER OPTION

Following study unblinding, subjects who had received the placebo device will be offered the opportunity to receive the same active course of treatment as was administered to subjects who had been assigned to the active device treatment group. Subjects who wish to engage in this option will re-commence the study at the study qualification evaluation phase. Given the nature of the condition, behavioral and functional change in either direction may be expected, and as such, study qualification and baseline evaluations will be redone for this cross-over subject group, with the exception of the DSM-IV-TR diagnosis confirmed with the ADI-R as both will be current within the past 2 years as per the study inclusion qualification criteria based upon the subject's initial enrollment on the study. Subjects will then proceed through the remainder of the course of the study as when they participated as a placebo subject and proceed to the post-procedure evaluation phase. Although these subjects and their caregivers will be aware that active treatment is being administered during this crossover phase, again by nature of the condition, the subjects are incapable of purposefully altering their behavior or function, so this will not impact the outcome of the placebo cross-over phase.

STATISTICAL ANALYSIS PLAN

The aim of this study is to determine if the treatment effect of the Erchonia® HLS laser device for the active treatment group is greater than that for the placebo treatment group.

The study will be considered a success if, using the Intent-To-Treat (ITT) Last Observation Carried Forward (LOCF) analysis, the primary endpoint is statistically significant at the 0.05 level.

PRIMARY EFFICACY OUTCOME MEASURE

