Abilify® (aripiprazole) Study: In the Abilify® study, the primary efficacy endpoint was the mean change from Baseline to Week 8 LOCF in the ABC Irritability Subscale score. There was a statistically significant difference between the treatment groups in favor of Abilify® (aripiprazole) in the adjusted mean change from Baseline to Week 8 LOCF (study Endpoint) in the ABC Irritability Subscale score of -7.9 (placebo -5.0, aripiprazole -12.9, difference -7.9, 95% CI (-11.7, -4.1), $p < 0.001$). It was concluded that this change demonstrated clinically relevant and statistically significant improvement compared with placebo on the primary efficacy endpoint in the adjusted mean change from Baseline on the ABC Irritability Subscale at Endpoint.

FDA independent analysis concluded that the results of the clinical trials showed that treatment with aripiprazole is efficacious in improving the symptoms of irritability in children and adolescents with autism, as demonstrated by the results on the primary endpoint, ABC Irritability Subscale. It was stated that **aripiprazole showed clinically meaningful and statistically significant improvement compared with placebo** through study Endpoint evaluation on the

primary efficacy measure of mean change from Baseline to Week 8 in the ABC Irritability Subscale score.

Erchonia® HLS Feasibility (Pilot) Study: A feasibility (pilot) study that employed the Erchonia® HLS Laser Device with the exact same device output parameters and treatment administration protocol as proposed for the current pivotal study was completed in September, 2012.

In the pilot study, eleven (9 male and 2 female) children and adolescents aged 5 years 4 months to 16 years 10 months with autistic disorder were enrolled according to the study qualification criteria proposed for the current pivotal clinical study. All subjects received the active procedure administrations with the actual Erchonia® HLS Laser Device. The Aberrant Behavior Checklist (ABC) assessment tool was administered at Baseline evaluation (before receiving the first laser treatment administration) and at study Endpoint (after completion of the laser treatment administration protocol).

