For subjects enrolled in this pilot study, the mean change from Baseline to study Endpoint in the Aberrant Behavior Checklist (ABC) Irritability Subscale score adjusted for Baseline ABC Irritability Subscale score was -9.09 (SD of change of 6.76). The mean Baseline ABC Irritability Subscale score was 14.45 (SD of 8.18) and the mean study Endpoint ABC Irritability Subscale score was 5.36 (SD of 6.70).

ANCOVA analysis for two correlated samples to evaluate the mean change from Baseline to study Endpoint in the Aberrant Behavior Checklist (ABC) Irritability Subscale score adjusted for Baseline ABC Irritability Subscale score found the mean change of -9.09 to be statistically significant at $p < 0.0005$ ($F = 23.27$; $p = 0.00012$).

Subsequently, based on the clinically significant results from the Abilify® clinical trial combined with the pilot study results from the Erchonia® HLS study demonstrating the predicted effect size of the Erchonia® HLS Laser Device and associated treatment administration protocol for the proposed indication, the midpoint in the change on the ABC Irritability Subscale score is determined to be -8.5 points, and the clinically significant study success for the currently proposed full-scale clinical study is defined as a minimum mean difference of -8.5 points on the ABC Irritability Subscale score from Baseline to Endpoint between active and placebo treatment groups.

Therefore, the estimated clinically significant effect size of the Erchonia® HLS Laser Device as applied to children and adolescents with autistic disorder in the proposed clinical study based on prior experience and research is a minimum mean difference of -8.5 points on the ABC Irritability Subscale score from baseline to endpoint (week four) between active and placebo treatment groups.

SECONDARY EFFICACY OUTCOME MEASURES

The following secondary efficacy outcome measures will be evaluated in this study:

- *Positive Response Rate*: Difference in Positive Response Rate between treatment groups, where 'Positive Response Rate' is defined as satisfaction of both of the following 2 criteria:
 - ✓ $\geq 25\%$ reduction from baseline to endpoint in the Aberrant Behavior Checklist (ABC) Irritability Subscale score based on the subject's primary caregiver's rating; AND
 - ✓ Clinical Global Impressions – Improvement (CGI-I) scale rating of 1 or 2 (much improved or very much improved) at study endpoint as determined by the clinician's evaluation

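### The plan has two conflicting success rules, and the -8.5-point minimum in one of them averages a placebo-controlled difference with an uncontrolled before-after change

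*Combined protocol and SAP*

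**What the plan says.** All places are in the combined protocol and SAP.

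- **Success, first statement.** The opening of Statistical Analysis Plan calls the study a success if, in the ITT LOCF analysis, "the primary endpoint is statistically significant at the 0.05 level". It sets no minimum difference.
- **Success, second statement.** Primary Efficacy Outcome Measure makes success depend on detecting a between-group difference of at least 8.5 points in favour of active treatment, and both the null and the alternative hypothesis carry that number. Rationale for Primary Efficacy Outcome Measure repeats it as the definition of clinically significant success.
- **Analysis.** Primary Efficacy Analysis specifies an ANCOVA with baseline and treatment. It describes no test against 8.5.
- **Origin of 8.5.** The rationale cites a placebo-controlled aripiprazole trial ("placebo -5.0, aripiprazole -12.9, difference -7.9, 95% CI (-11.7, -4.1") and the device pilot, whose change "score adjusted for Baseline ABC Irritability Subscale score was -9.09 (SD of change of 6.76". In the pilot, "all subjects received the active device treatments". It concludes: "the midpoint in the change on the ABC Irritability Subscale score is determined to be -8.5 points".
- **Sample size.** Rationale and Justification for Sample Size begins "Based on detecting a mean difference of -8.5 points between test and placebo groups", takes an SD of 8.9, and states: "a two-sided test with 80% power and a 5% level of significance, the number of subjects needed per treatment group is 18". After dropout, "a minimum starting sample size of 20 subjects in each treatment group (40 subjects in total) is needed".

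**The concern.** Two rules that can give opposite answers on the same data are both in force. A significant difference smaller than 8.5 points is a success under the first statement and can be a failure under the second. The plan does not say which governs, and this is a pivotal study meant to support a de novo application. The stated power is also attached to a success definition that it may not describe.

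The number itself has a weak basis. The -7.9 is a difference from placebo. The -9.09 is a before-after change in 11 children, all on active device, so it contains whatever placebo response, regression to the mean and time trend the pilot had. The wording about baseline adjustment does not change this: 14.45 - 5.36 = 9.09, so the figure is the raw mean change. The average of the two is nevertheless used as the expected active-minus-placebo difference.

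**Working it through.** Differences are given as size of benefit. Inputs: difference 8.5, SD 8.9, two-sided 5%, 80% power, 18 evaluable and 20 enrolled per arm (Rationale and Justification for Sample Size); 7.9 and 9.09 (Rationale for Primary Efficacy Outcome Measure).

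**1. The plan's own figures reproduce.** n per arm = 2 × (8.9/8.5)² × (1.960 + 0.842)² = 17.2, rounded up to 18. An exact t calculation gives 19. For dropout, 18/0.89 = 20.2, which the plan reports as 20.

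**2. The midpoint.** (7.9 + 9.09)/2 = 8.495, the plan's 8.5. If the pilot's unobserved placebo change was p points, putting both figures on the placebo-adjusted scale gives (7.9 + 9.09 - p)/2 = 8.495 - p/2. This equals the plan's value only when p = 0.

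**3. Power of the significance rule.** Noncentral t with 2n - 2 degrees of freedom and noncentrality d/(8.9 × √(2/n)):

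| True difference | 18 per arm | 20 per arm |
|---|---|---|
| 8.5 | 79% | 84% |
| 7.9 | 73% | 78% |

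The plan's normal approximation gives 76% and 80% at 7.9. Both sample sizes are shown because LOCF may keep the analysed number near 20.

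**4. Where the two rules part.** The standard error is 8.9 × √(2/n) = 2.97 (n = 18) or 2.81 (n = 20). The smallest significant observed difference is t(0.975) × SE:

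- n = 18: 2.032 × 2.967 = 6.03
- n = 20: 2.024 × 2.814 = 5.70

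Observed differences from there up to 8.5 are significant but short of the minimum. Treating the estimate as normal with this SE:

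| True difference | Chance observed is at least 8.5 (n = 18 / 20) | Chance significant but below 8.5 (n = 18 / 20) |
|---|---|---|
| 8.5 | 50% / 50% | 30% / 34% |
| 7.9 | 42% / 42% | 32% / 37% |

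An 80% chance of observing at least 8.5 with 18 per arm would need a true difference of 8.5 + 0.842 × 2.967 = 11.0.

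**5. Sensitivity to the pilot's placebo response (assumption).** The documents give no value for p. Over a range of 0 to 5 points, where 5.0 is the drug trial's 8-week placebo change, step 2 gives 8.495 falling to 5.995. The power formula of step 3 then falls from 79% to 50% with 18 per arm, and from 84% to 55% with 20.

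**The case against.** **The 8.5 may be a clinical-relevance target, not a forecast.** A target need not be an unbiased estimate, and 8.5 lies inside the drug trial's confidence interval of 4.1 to 11.7. That stands as far as it goes: the value is plausible. But the rationale also calls it the device's estimated effect size, and as a relevance threshold it sits above the 7.9 that the same section describes as clinically relevant.

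**The sponsor may want a minimum effect.** The outcome section and the rationale both state it, and only the opening section omits it. This stands: the documents do not show which rule was intended, so removing the minimum is not the only acceptable repair. Keeping it, however, means that 80% is not the power of the trial.

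**The power shortfall depends on one SD.** This also stands. The plan does not say whether 8.9 is before or after baseline adjustment. If before, and assuming a baseline-change correlation of 0.4, the residual SD is 8.9 × √(1 - 0.16) = 8.16 and power at 7.9 is 81% (18 per arm) or 85% (20 per arm). With the pilot's SD of 6.76 it would be 93% or 95%, although 11 children do not make that a better planning value.

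**Stronger readings that a reader might infer.**

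- *The trial has only about even odds of success under the significance rule.* This takes the worst end of step 5, which carries a placebo change from an 8-week drug trial into a 4-week device pilot. The documents cannot support any single value.
- *The hypotheses call for a formal test against 8.5.* Taken literally they would need an observed difference of about 8.5 + 1.96 × 2.97 = 14.3 with 18 per arm, but no such test is specified.
- *The pilot did not use this trial's entry criteria, because its mean baseline of 14.45 is below the threshold of 18.* The plan scores the ABC both at qualification and at baseline, the pilot's qualification scores are not in the text available, and part of the pilot report is missing from that text. The inference is not established.

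**Conclusion.** The conflict between success rules holds on the text and is the main point. If 8.5 must be observed, about three trials in ten with 18 per arm (30%), or one in three with 20 (34%), would be significant yet fail the minimum when the true difference is exactly 8.5. The chance of meeting the minimum is then about 50%. The 80% power and the specified ANCOVA match only the significance rule.

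The derivation of 8.5 is also unsound as a between-group estimate, since it assumes a zero placebo response in the pilot. The demonstrable consequence is modest: 73% or 78% power at the controlled difference of 7.9, against 79% or 84% at 8.5. This is conditional on SD 8.9, and power is higher if that SD is before baseline adjustment. The sample-size arithmetic is not in error.

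The plan should be corrected before unblinding. Confidence is high for the conflict and the mixed midpoint, and lower for the size of any power loss.

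**What to change.** 1. **One success rule** in Statistical Analysis Plan, Primary Efficacy Outcome Measure and its rationale. The rule that fits the sample-size calculation and the ANCOVA is the two-sided 5% test. Restate the hypotheses as adjusted mean difference equal to zero versus not equal to zero, and keep 8.5 only as a planning or interpretive value. If the sponsor keeps 8.5 as a required minimum, say whether it must be observed and replace the 80% with the power of that rule (about 50% at a true 8.5).
2. **Rationale for Primary Efficacy Outcome Measure.** Label -9.09 as an uncontrolled before-after change in 11 children. Stop presenting the midpoint as an estimated active-minus-placebo effect, and state -8.5 as an assumption beside the controlled -7.9. If a pilot placebo response is discussed, show a range such as 0 to 5 points and label it an assumption.
3. **Rationale and Justification for Sample Size.** Keep 40 subjects and report t-based power at both differences (79% or 84% at 8.5; 73% or 78% at 7.9, with 18 or 20 analysed per arm). State that this assumes SD 8.9 and whether that SD is baseline-adjusted.

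The cost is text edits and a four-cell table. Enrolment changes only if the sponsor wants to claim 80% at 7.9. By the plan's method that needs 2 × (8.9/7.9)² × (1.960 + 0.842)² = 19.9, so 20 evaluable per arm, and 20/0.89 = 22.5, so 22 to 23 enrolled per arm.

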- Mean change from baseline to endpoint in the other 4 ABC Subscale scores, based on ratings by the subject's primary caregiver:
 - ✓ Lethargy/Social Withdrawal
 - ✓ Stereotypic Behavior
 - ✓ Hyperactivity/Noncompliance
 - ✓ Inappropriate Speech
- Mean change from baseline to endpoint in the global ABC score
- Change in ratings on the CGI-S from baseline to study endpoint evaluation
- Change in ratings on the CGI-I from baseline to study endpoint evaluation

STATISTICAL METHODS

Efficacy analysis will be according to the intent to treat (ITT) principle by last observation carried forward (LOCF).

Intent to Treat: Subjects will be included in the ITT analysis if they complete their baseline clinical assessments and had at least one post-randomization efficacy evaluation and corresponding baseline value.

Last observation carried forward (LOCF): Missing data will be handled by carrying forward the last observation for the relevant measure. The LOCF data set included data recorded at a given time point, or, if no observation was recorded at that time point, data carried forward from the previous time point with available data. Baseline data will not be carried forward or averaged to impute missing values for the LOCF data set.

STATISTICAL ANALYSIS

Primary Efficacy Analysis

For the continuous primary efficacy measure of ABC Irritability Subscale score, change scores will be evaluated by analysis of covariance (ANCOVA). The ANCOVA models for LOCF data sets will include the baseline measure as a covariate and treatment (active of placebo) as main effects.

Secondary Measures Analysis

- For the continuous secondary efficacy measures of the other 4 ABC Subscale scores, and the Global Score, change scores will be evaluated by analysis of covariance (ANCOVA). The ANCOVA models for LOCF data sets will include the baseline measure as a covariate and treatment (active of placebo) as main effects. A two-way significance level of 5% will be considered to be statistically significant.

- For the categorical measures of the CGI will be analyzed within the framework of the generalized Cochran-Mantel Haenszel (CMH) procedure.
- Responder rate will be evaluated using Fisher's exact test to compare the proportion of responder rates between the test and control groups.

P-values will be 2-tailed tests of significance rounded to 3 decimal places. All analyses will be performed at the 5% significance level.

SAFETY ANALYSES

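### The Positive Response Rate leaves out treated children who withdraw before the first on-treatment rating, so the comparison is conditional on staying to the end of Week 2

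*Combined protocol and SAP*

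**What the plan says.** The STATISTICAL METHODS section places efficacy analysis as a whole under intent to treat with last observation carried forward (LOCF). Its Intent to Treat paragraph admits subjects who completed baseline and "had at least one post-randomization efficacy evaluation and corresponding baseline value". A missing value is replaced by "data carried forward from the previous time point with available data", with one limit: "Baseline data will not be carried forward or averaged to impute missing values for the LOCF data set".

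Under SECONDARY EFFICACY OUTCOME MEASURES, Positive Response Rate "is defined as satisfaction of both of the following 2 criteria". The first is a fall of at least 25% in ABC Irritability to endpoint on the caregiver's rating. The second is a CGI-I "scale rating of 1 or 2 (much improved or very much improved) at study endpoint as determined by the clinician's evaluation". Under Secondary Measures Analysis the test is given as follows: "Responder rate will be evaluated using Fisher's exact test to compare the proportion of responder rates between the test and control groups". No separate analysis set, rule for unrated children or sensitivity analysis is given for this endpoint.

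The STUDY EVALUATION TIMELINE puts the first on-treatment ABC and CGI ratings at the end of Week 2, after the first four treatments. SAFETY ANALYSES uses a wider set: every randomised subject who received at least the first treatment.

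**The concern.** A child who has one to three sessions and then leaves has no post-treatment rating and nothing that may be carried forward. The child is counted for safety but is absent from the response rate. Whether a child stays to the end of Week 2 is settled after randomisation and could depend on the assigned device, for example through lack of benefit. The response comparison is then between those who stayed, not between the groups as treated.

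A continuous change score needs an imputed number for an unrated child. A yes/no endpoint does not: the child can be counted as not having shown a response. With 20 children per arm, even a few such exclusions can move the rates and the p-value. At stake is the interpretation of one secondary endpoint.

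**Working it through.** **Inputs from the documents.** There are 20 children per arm, 40 in total (Subject Sample Size). About one-tenth overall are expected to withdraw before completion (Rationale and Justification for Sample Size). The first on-treatment rating is at the end of Week 2. The test is Fisher's exact test, two-tailed, at 5%.

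**The plan's own figure.** The plan states no rate, power or sample size for the Positive Response Rate. Its only sample size is for the primary endpoint. The normal-approximation formula is n = 2 × [SD × (z₀.₉₇₅ + z₀.₈₀) / difference]². With SD 8.9 and difference 8.5 this gives 17.2, so 18 per arm. Inflation gives 18 / 0.89 = 20.2, which the plan takes as 20. These figures reproduce, and this point does not alter them.

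**Number of children affected.** One-tenth of 40 is 4. That allowance covers the whole study, and the share leaving before Week 2 is not given. The number affected is therefore between 0 and about 4.

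**Formulas.** Let a and b be the responders on active and placebo, and let u and v be the treated children with no rating in each arm. All 20 per arm are taken as treated.
- Rule as written: a/(20 − u) v b/(20 − v).
- Unrated counted as non-responders: a/20 v b/20, whatever u and v are.

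The documents give no response rates, so a and b below are assumptions.

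**Assumed 12 active and 6 placebo responders.** Counting leavers as non-responders gives 12/20 v 6/20 (60.0% v 30.0%), difference 30.0 points, p = 0.111 for every split.

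| Unrated leavers (active, placebo) | Rule as written | Difference (points) | p |
|---|---|---|---|
| 2, 0 | 12/18 v 6/20 | 36.7 | 0.0496 |
| 2, 1 | 12/18 v 6/19 | 35.1 | 0.0502 |
| 1, 0 | 12/19 v 6/20 | 33.2 | 0.056 |
| 1, 1 | 12/19 v 6/19 | 31.6 | 0.103 |
| 2, 2 | 12/18 v 6/18 | 33.3 | 0.094 |
| 0, 2 | 12/20 v 6/18 | 26.7 | 0.119 |

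**Assumed 10 active and 4 placebo responders, four leavers in all.** Counting leavers as non-responders gives 10/20 v 4/20 (50.0% v 20.0%), difference 30.0 points, p = 0.096 for every split.

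| Unrated leavers (active, placebo) | Rule as written | Difference (points) | p |
|---|---|---|---|
| 4, 0 | 10/16 v 4/20 | 42.5 | 0.016 |
| 3, 1 | 10/17 v 4/19 | 37.8 | 0.039 |
| 2, 2 | 10/18 v 4/18 | 33.3 | 0.086 |
| 1, 3 | 10/19 v 4/17 | 29.1 | 0.097 |
| 0, 4 | 10/20 v 4/16 | 25.0 | 0.176 |

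Balanced leaving changes the p-value little. Leaving concentrated on active enlarges the apparent difference, and leaving concentrated on placebo shrinks it.

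**The case against.** Several points on the other side stand.

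- **Imbalance is not shown.** The plan predicts neither an imbalance nor a share of leavers before Week 2. Sessions last five minutes at four inches from the skin. The sham looks the same and emits the same visible light, and neither device gives notable heat or noise. Leaving because the active sessions are poorly tolerated has little support in the documents. Lack of benefit remains a possible reason.
- **Direction.** A reader might infer that the rule favours the device, or that one or two children will decide significance. The documents support neither. The bias can run both ways. In the 12 v 6 example, p falls below 0.05 only when both leavers are on active and none on placebo, and then only just.
- **The response definition.** A reader might infer that the definition itself makes an unrated child a non-responder. It does not: it speaks of endpoint ratings, and a child without them is unclassified. Counting that child as a non-responder is a defensible convention, but it has to be added.
- **Importance.** This is one of several secondary measures. The same set is used for the primary ANCOVA.

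One possible escape fails. SUBJECT GROUP RANDOMIZATION and the TABLE OF SUBJECT EVENTS list randomisation before qualification and baseline, so a baseline rating is literally made after randomisation. But the Intent to Treat paragraph asks for a corresponding baseline value as well, so the evaluation it has in mind is a later one. Even if the child were admitted on that reading, there would be no endpoint value from which to judge response.

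**Conclusion.** The point holds in a limited form. As written, the Positive Response Rate excludes any treated child who leaves before the end-of-Week-2 rating, and nothing elsewhere in the plan restores that child. The link to the efficacy set comes from the general statement on efficacy analysis, since the sentence on Fisher's test names no set of its own.

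The size cannot be fixed from the documents. It rests on assumed responder counts and on 0 to about 4 affected children. Within that range, the 10 v 4 example runs from p = 0.016 to 0.176 under the rule as written, against 0.096 when leavers count as non-responders. If no child leaves that early, nothing changes.

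Study success under STATISTICAL ANALYSIS PLAN rests on the primary endpoint and is not touched. The change is worth making because it is cheap and removes an avoidable dependence on early retention. Children who have a Week 2 rating and then leave remain in the set through LOCF; that is a separate matter.

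**What to change.** Before unblinding, add to Secondary Measures Analysis that the Positive Response Rate is analysed in all randomised subjects who received at least one treatment, the set already defined under SAFETY ANALYSES. Any subject lacking a post-baseline ABC Irritability or CGI-I rating counts as a non-responder. Keep the present ITT-LOCF version as a sensitivity analysis, and report the number of unrated children by arm.

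This set is still a subset of those randomised, because randomisation is listed before qualification and some children may never be treated. Leaving before treatment, while the assignment is blinded, is unlikely to depend on the device.

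The cost is a sentence or two in the plan, with no new data, visits or subjects. The downside is that stated response rates will be slightly lower wherever there are unrated leavers.
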